7. CHILD PARTICIPANT ENTRY

7.1. PRE-REGISTRATION EVALUATIONS AND RECRUITMENT

This is a pragmatic, observational study involving preschool children with wheeze aged one to five years old. All treatment and routine monitoring decisions will be at the discretion of their treating general practitioner (GP) or paediatrician (as per usual clinical practice), blinded to the study measurements. After clinical consultation and following submission of the electronic informed consent through the Qualtrics® questionnaire platform (offered by Imperial College London), the parent/carer will be asked to give the contact details of the child's GP or paediatrician, who will be informed about child's participation in this study through a letter sent to his/her email along with the patient information sheet. The parent carer will be then shown a standard video questionnaire and will be asked to identify what respiratory sounds their children have been making. The child will be booked for the three biomarker tests [atopic sensitisation, blood eosinophil count and FeNO (off-line method)]. The tests will be carried out once and at a time of clinical stability. In this visit, a sample of the child's exhaled tidal breath will be collected in a suitable bag in duplicate for offline

measurement of FeNO later on with chemiluminescence. Skin prick tests will be performed to: (a) house dust mite, (b) grass pollen, (c) tree pollen, (d) cat hair, (e) dog hair, as well as normal saline and histamine and these will be applied on either the child's back, leg or arm. If the child has been prescribed antihistamines, we will ask for these to be withheld for 72 hours prior to skin prick testing. FeNO values (offline method) ≥ 10 ppb will indicate Type 2 inflammation and wheal diameter, measured with a specialised skin prick test ruler, ≥ 3 mm will indicate sensitisation to the applied aeroallergen. In addition, skin prick tests will allow the assessment of which aeroallergen is the most useful predictor of outcomes in preschool children. Finally, the peripheral blood eosinophil count will be measured from a finger prick blood sample, using the Haemocue machine, allowing a result in approximately 2 minutes. Values ≥ 300 cells/ μ l indicate Type 2 inflammation. All tests will normally take no more than one hour.

The recruitment period will approximately last 9 months, and all preschool wheezers can join the study at any point (Appendix 1: Recruitment Plan). Parents/Carers of preschool children presenting to primary care or to the Emergency Department (ED) or secondary care (e.g., outpatients) as well as those identified from primary care records and who have been diagnosed by a GP or paediatrician with wheezing, will be approached by collaborating doctors and nurses who will ask their parents if they are willing to have their child participate in the study (Appendix 1 – Recruitment Plan). A patient information sheet will be given, containing all the information regarding the project and the contact details of the research team, for further questions. They will be asked for their willingness to give the study team permission to contact them and discuss recruitment, and if so, they will submit their contact details in an electronic form made with the Qualtrics® questionnaire platform (offered by Imperial College London), which allows gathering data according to the GCP guidelines and as used for years in the Breathing Together study (19). This form will be available online in the Asthma UK Centre for Applied Research's (AUKCAR) website. The initial introduction will be made either by the clinical team (above) with the study team contacting them at a later date to give more information or by [name] if he is there in person. If the child has been prescribed OCS, testing will be delayed by 2 weeks for biomarker testing as soon as the electronic informed consent is submitted. Finally, parents will be informed through the patient information sheet as well as, in person, that a second optional testing will take place 3 months after the first one, in their second study visit. This will allow assessing the reproducibility of the obtained biomarker results, thus additionally assess their stability.

Patient recruitment at a site will only commence once the study team has ensured the following:

- HRA approval
- Completed Local Site Delegation of Duties and Signature Log
- Confirmation of Capacity and Capability

All recruitment procedures will be in accord with the GCP, and parents/carers will be given detailed information regarding the study as well as all the time they need to understand it. Parents/guardians have at least 24 hours to consider participation. Recruitment will only commence after parents/carers have fully understood the project and submitted the electronic informed consent form through the Qualtrics® platform (offered by Imperial College London).

Child participants entering the study upon their parents' wish, will be fully screened by the Principal Investigator (PI) or someone else from the research team who is suitably qualified and delegated to do so, with the latter taking informed consent as well. After the electronic informed consent sheet is submitted, parents will be asked to provide the contact details of their child's GP or paediatrician, to inform him/her about the child's participation in this study through a letter sent by email along with this patient information sheet. In addition, we will ask them to provide some of the child's personal data (Appendix 1: Recruitment Plan, Table 3: The personal data that will be obtained by each individual participant). Children's full name, date of birth, gender, ethnicity as well as, their parent's full name, telephone number and email address will be added in the child's patient card. All other data obtained from the study will be added in the Case Report Form (CRF).

Follow-up: We will arrange for a short monthly electronic questionnaire to be sent by email to the parents/carers, in order to record on a monthly basis, the days their child was out of childcare, days the carer missed from work, unscheduled health care visits and use of rescue therapy or oral corticosteroids (including dosage) (Appendix 4: Monthly Questionnaire). In addition, we will record the children's TRACK™ score (Test for Respiratory and Asthma Control in Kids) (Appendix 3: TRACK™ score questionnaire) every 3 months, to assess wheeze control. The questionnaires will be made and sent through the Qualtrics® questionnaire platform (offered by Imperial College London). There will be review visits every 3 months, to evaluate their progression in person, but if not feasible, video calls will be arranged through Microsoft Teams. Correct use of spacers will be ensured after guiding parents on how to use them and will be done by their GP or paediatrician as well as from [name] who is a registered pharmacist in the UK.

In the event that a child has had their ICS treatment discontinued, we will record whether this was because the treatment was ineffective (treatment failure) or if the child was so well that the family or GP did not wish to continue (treatment success or spontaneous improvement). If an additional medication is prescribed, or the child is referred to secondary care, this will be considered as treatment failure. When the study ends, participants' parents/carers will be invited to a face-to-face focus group interview, or a one-to-one interviews, or remotely through Microsoft Teams, depending on their availability at the end of the study period. The focus group and one to one interviews will utilise a semi structured questionnaire, to provide qualitative

feedback on the acceptability of the 3 biomarker tests. In addition, a separate focus group for doctors and nurses will be conducted to assess the feasibility of the 3 biomarker tests being used in clinical practice. They will be given all the information regarding the study as well as the study's patient information sheet. Those agreeing to take part, will sign a consent form. They will be attending either a face-to-face focus group interview, or a one-to-one interview, or remotely through Microsoft Teams, depending on their availability. A semi structured questionnaire will be utilised. Where possible a second independent researcher will sit in the focus groups discussion and interviews to ensure there is no bias. The conversations from the focus group and one to one interviews will be transcribed and coded into themes. We will utilise an external company for transcribing the conversations called 1st Class. <https://www.1stclass.uk.com/>

The focus group and one-to-one interviews will be audio recorded, transcribed and put into themes to conduct an inductive thematic analysis. 25% of the transcripts will be double coded by an independent researcher, experienced in qualitative research to ensure that the correct themes have been used and to ensure that there is no bias. The focus group and one to one interviews will be used to assess the acceptability and feasibility of measuring biomarkers in primary care and using them to help determine management of preschool wheeze.

In addition, we will ask them to fill in a very short electronic questionnaire after the study is finished, to check their perspective and acceptability on these biomarkers being used to guide children's therapy in the future (Appendix 5: Exit Questionnaire).

The whole duration of this study is expected to be 20-21 months, with 1-year follow-up for each patient included.

7.2. INCLUSION AND EXCLUSION CRITERIA

7.2.1. CHILDREN

INCLUSION CRITERIA	EXCLUSION CRITERIA

1. Patients aged one to five years old presenting to primary care or to the emergency department or to secondary care (e.g., outpatients) or identified from primary care records and have been diagnosed with wheezing by their GP or paediatrician who has decided to prescribe any bronchodilator, ICS or montelukast on clinical grounds
	
1. Inability to understand and cooperate with study procedures
 
2. Significant co-morbidity (respiratory or otherwise), for example cystic fibrosis (excluding atopic disorders such as eczema, allergic rhinitis and food allergy)
 
3. Withholding or withdrawal of informed consent

2. Parents/Carers able to understand and familiarize themselves with the study and are willing to provide informed consent
	
4. Severe procedural anxiety (needle phobia)
 
5. Child is already enrolled in another study involving investigational medicinal product (CTIMP)
 
6. History of near-fatal asthma that resulted in intubation / assisted ventilation.

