project and the contact details of the research team, for further questions. They will be asked for their willingness to give the study team permission to contact them and discuss recruitment. After clinical consultation and following submission of the electronic informed consent, the parent/carer will be asked to give the contact details of the child's GP or paediatrician, who will be informed about child's participation in this study through a letter sent to his/her email along with the patient information sheet. In addition, we will ask them to provide some of the child's personal data. The parent carer will be then shown a standard video questionnaire and will be asked to identify what respiratory sounds their children have been making. The child will be booked for the above biomarker tests at a single visit and at a time of clinical stability. If the child has been prescribed OCS, biomarker testing will be delayed by 2 weeks. Firstly, a sample of the child's exhaled tidal breath will be collected in a suitable bag for offline measurement of FeNO. Skin prick tests will be performed to (a) house dust mite, (b) grass pollen, (c) tree pollen, (d) cat hair € dog hair, as well as negative and positive controls and these will be applied on either the child's back, leg or arm. If the child has been prescribed antihistamines, we will ask for these to be withheld for 72 hours prior to skin prick testing. Finally, the peripheral blood eosinophil count will be measured from a finger prick blood sample, using the Haemocue machine, giving a result in approximately 2 minutes. All tests will normally take no more than one hour.

[figure not shown]

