The Lancet Asthma Commission has highlighted that 'asthma' is an umbrella term for a clinical syndrome comprising wheeze, chest tightness, breathlessness and sometimes increased cough (2). The focus has moved to defining so-called 'treatable traits', such as whether there is eosinophil airway inflammation, usually driven by the signature Type 2 cytokines Interleukin (IL) -4, -5, and -13, which are responsive to inhaled corticosteroids (ICS) (6,7). Nowhere is this concept of treatable traits more important than in preschool wheeze, wherein only a few children who wheeze have any evidence of allergic sensitisation or Type 2 inflammation. At age one year, even children with such severe symptoms as to merit bronchoscopy in a tertiary referral children's hospital had no evidence of any inflammation or airway remodelling (8). By 30 months of age, in another cross-sectional study, some but by no means all had evidence of eosinophil airway inflammation, reticular basement membrane thickening and airway smooth muscle hypertrophy and hyperplasia (9). Clinical experience reflects this diversity, and although atopic preschool wheezers are more likely to respond to ICS, as we have shown, many atopic wheezers do not have an eosinophil airway phenotype (10), and are thus unlikely to be ICS responsive. We have recently confirmed that there is a good correlation between bronchoalveolar lavage and peripheral blood eosinophil concentrations (11).

Another biomarker for eosinophil airway inflammation is exhaled nitric oxide (FeNO). In older children and adults, titrating ICS dose using FeNO has been shown to reduce asthma attacks and improve outcomes (12). The use of FeNO to guide management not been studied in pre-school children. Young children usually cannot perform the standard slow exhalation, but we have experience in measuring FeNO off-line by collecting tidally exhaled air, which is the technique we propose to use.

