6. STUDY DESIGN

This is a pragmatic, observational study involving preschool children with wheeze aged one to five years old. All treatment and routine monitoring decisions will be at the discretion of their treating general practitioner (GP) or paediatrician (as per usual clinical practice), blinded to the study measurements. After clinical consultation and following submission of the electronic informed consent through the Qualtrics® platform (offered by Imperial College London), the parent/carer will be asked to give the contact details of the child's GP or paediatrician, who will be informed about child's participation in this study through a letter sent to his/her email along with the patient information sheet. The parent carer will be then shown a standard video questionnaire and will be asked to identify what respiratory sounds their children have been making. The child will be booked for the three biomarker tests [atopic sensitisation, blood eosinophil count and FeNO (off-line method)]. The tests will be carried out once and at a time of clinical stability. In this visit, a sample of the child's exhaled tidal breath will be collected in a suitable bag in duplicate for offline measurement of FeNO later on with chemiluminescence. Skin prick tests will be performed to: (a) house dust mite, (b) grass pollen, (c) tree pollen, (d) cat hair(e) dog hair, as well as normal saline and histamine and these will be applied on either the child's back, leg or arm. If the child has been prescribed antihistamines, we will ask for these to be withheld for 72 hours prior to skin prick testing. FeNO values (offline method) ≥ 10 ppb will indicate Type 2 inflammation and wheal diameter, measured with a specialised skin prick test ruler, ≥ 3 mm will indicate sensitisation to the applied aeroallergen. In addition, skin prick tests will allow the assessment of which aeroallergen is the most useful predictor of outcomes in preschool children. Finally, the peripheral blood eosinophil count will be measured from a finger prick blood sample, using the Haemocue machine, allowing a result in approximately 2 minutes. Values ≥ 300 cells/ μ l indicate Type 2 inflammation. All tests will normally take no more than one hour.

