If the child has been prescribed OCS, testing will be delayed by 2 weeks for biomarker testing as soon as the electronic informed consent is submitted. Finally, parents will be informed through the patient information sheet as well as, in person, that a second optional testing will take place 3 months after the first one, in their second study visit. This will allow assessing the reproducibility of the obtained biomarker results, thus additionally assess their stability.

Patient recruitment at a site will only commence once the study team has ensured the following:

- HRA approval
- Completed Local Site Delegation of Duties and Signature Log
- Confirmation of Capacity and Capability

All recruitment procedures will be in accord with the GCP, and parents/carers will be given detailed information regarding the study as well as all the time they need to understand it. Parents/guardians have at least 24 hours to consider participation. Recruitment will only commence after parents/carers have fully understood the project and given informed consent online through the Qualtrics® platform (offered by Imperial College London).

Child participants entering the study upon their parents' wish, will be fully screened by the Principal Investigator (PI) or someone else from the research team who is suitably qualified and delegated to do so, with the latter taking informed consent as well. After the electronic informed consent sheet is submitted, parents will be asked to provide the contact details of their child's GP or paediatrician, to inform him/her about the child's participation in this study through a letter sent by email along with this patient information sheet. In addition, we will ask them to provide some of the child's personal data (Appendix 1: Recruitment Plan, Table 3: The personal data that will be obtained

by each individual participant). Children's full name, date of birth, gender, ethnicity as well as, their parent's full name, telephone number and email address will be added in the child's patient card. All other data obtained from the study will be added in the Case Report Form (CRF).

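### ICS status at testing enters neither the timing, the classification nor the analysis of the biomarkers, so treated and untreated children are mixed under one set of cut-offs

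*Combined protocol and SAP*

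**What the plan says.** **Who enters.** Section 7.2.1 takes children aged one to five whose GP or paediatrician has diagnosed wheeze and "who has decided to prescribe any bronchodilator, ICS or montelukast on clinical grounds". They present to care, "or identified from primary care records and have been diagnosed with wheezing by their GP or paediatrician". No exclusion criterion mentions ICS.

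**When they are tested.** Section 7.1 describes the sequence that leads to the tests as "After clinical consultation and following submission of the electronic informed consent". The tests are then booked for a time of clinical stability, with no stated interval from the prescribing decision.

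**Which drugs have a timing rule.** There are two: "If the child has been prescribed OCS, biomarker testing will be delayed by 2 weeks" (Study Summary) and "If the child has been prescribed antihistamines, we will ask for these to be withheld for 72 hours prior to skin prick testing" (Section 7.1).

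**How children are classed.** "FeNO values (offline method) ≥ 10 ppb will indicate Type 2 inflammation" (Section 6), and 300 eosinophils/µl or more is read the same way. Both cut-offs apply to every child.

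**Retest.** An optional second test at 3 months has a stated purpose: "This will allow assessing the reproducibility of the obtained biomarker results" (Section 6), and with it stability.

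**Analysis.** Section 11 lists chi-squared, Fisher's exact, t and Mann-Whitney tests. ICS is neither a stratum nor a covariate.

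**The concern.** The plan accepts that drugs can disturb these tests, since it protects them from oral steroid and antihistamines. It makes no provision for ICS, which its own entry criterion names.

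Section 4.1 says that type 2 eosinophilic airway inflammation responds to ICS, presents FeNO as a biomarker of it, and reports that in older children and adults "titrating ICS dose using FeNO has been shown to reduce asthma attacks and improve outcomes". On that reasoning, two children with the same underlying inflammation, one on ICS and one not, can be classed differently by the same cut-off.

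Three outputs are exposed:
- **Association with attacks.** If type 2 children sit in the negative group because of treatment, the contrast between groups shrinks. Section 4.2 hopes to spare non-responders from ICS, so a negative result that treatment produced is the error that matters most for that aim.
- **Positivity rates.** Section 4.3 wants pilot data for the power calculation of the later trial. A rate that blends treated and untreated children may not carry over to a trial that tests children before treatment.
- **Reproducibility.** If ICS is started or stopped between the two tests, a real change cannot be told from measurement instability.

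**Working it through.** **Plan's own figure.** There is none to reproduce. The target of 100 children has no stated power, effect size, event rate, biomarker prevalence or share on ICS.

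**Reading check.** Entry allows ICS, testing follows the prescribing decision, timing rules cover two other drug classes, the cut-offs are common to all, and the listed tests are unadjusted. These statements are consistent across the Study Summary and Sections 6, 7.1, 7.2.1 and 11.

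**Illustration of size for FeNO.** Every input except the 10 ppb cut-off is an assumption: log-normal FeNO in type 2 children with geometric SD 1.8 and untreated median 14 or 20 ppb; 40% of children type 2; one-year attack risk 60% (type 2) and 30% (others); specificity 90%; 50-70% of type 2 children on ICS at the test; FeNO lowered by 20-50% on ICS; attack risk not altered by ICS.

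Share of type 2 children below the cut-off: P = Φ( ln[10 / (median × (1 − fall))] / ln 1.8 ).

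Sensitivity = 1 − [(1 − s) × P(no fall) + s × P(fall)], where s is the share of type 2 children on ICS.

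Risk in positives = (0.4 × sens × 0.6 + 0.06 × 0.3) / (0.4 × sens + 0.06).

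Risk in negatives = (0.4 × (1 − sens) × 0.6 + 0.54 × 0.3) / (0.4 × (1 − sens) + 0.54).

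*No ICS effect on the test, median 14.* P = Φ(−0.3365/0.5878) = 0.2835, so sensitivity is 0.7165. Risks are 0.548 and 0.352, ratio 1.56.

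*50% fall, 70% on ICS, median 14.* P = Φ(0.3567/0.5878) = 0.728. Sensitivity = 1 − (0.3 × 0.2835 + 0.7 × 0.728) = 0.405. Risks are 0.519 and 0.392, ratio 1.32.

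| Fall in FeNO on ICS | Below 10 ppb (median 14) | Observed risk ratio | Below 10 ppb (median 20) | Observed risk ratio |
|---|---|---|---|---|
| none | 28% | 1.56 | 12% | 1.72 |
| 20% | 42% | 1.48-1.50 | 21% | 1.65-1.67 |
| 35% | 56% | 1.41-1.45 | 33% | 1.57-1.61 |
| 50% | 73% | 1.32-1.39 | 50% | 1.48-1.54 |

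The lower end of each range is 70% on ICS, the upper end 50%.

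**Positivity rate.** Apparent positivity is 0.4 × sens + 0.06. At median 14 it falls from 35% to 22-32%, and at median 20 from 41% to 31-39%. This part does not depend on the attack risks.

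**If ICS also lowers attacks.** Suppose treated type 2 children have a 40% risk. At median 14 with 70% on ICS and no effect on FeNO, positives are 0.086 untreated type 2, 0.201 treated type 2 and 0.060 false positive, with risk 0.432. Negatives are 0.034, 0.079 and 0.540, with risk 0.328. The ratio is 1.32. With a 50% fall in FeNO the treated children split 0.076 positive and 0.204 negative, the risks become 0.450 and 0.339, and the ratio is 1.33. Here the fall in FeNO adds almost no attenuation, because treatment has already lowered the ratio. The mixing of treated and untreated children remains.

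**The case against.** The study is a pragmatic, observational pilot. If the target is prediction under usual care, an on-treatment value is a legitimate predictor, and a low value on ICS may correctly signal lower risk. The last calculation shows that this has force: loss of predictive strength through misclassification is conditional, not established. It does not answer the point about positivity rates or the retest, nor the need to know which children a result describes.

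Stronger readings are tempting, and the documents do not support them:
- **That treated type 2 children are misread as negative.** The documents support only that they can be. The titration evidence in Section 4.1 concerns older children and adults, and the same section says that FeNO-guided management has not been studied in preschool children. For blood eosinophils the support is weaker still: a reported correlation with lavage eosinophils, and no statement that ICS shifts the 300/µl class.
- **That ICS use is not recorded.** Table 3 of Appendix 1 and the CRF are not in the text available for this review. Appendix 4, question 4, asks monthly about steroid dose, frequency and duration, so some information exists by the month-3 retest. Section 6 records why ICS was discontinued, and Section 13.5 seeks access to medical notes. The real weakness is that question 4 pools inhaled with oral steroid.
- **That the retest will count ICS changes as poor reproducibility.** The plan states no reproducibility statistic or counting rule. Such changes can look that way if ICS status is ignored.
- **That the false negatives concentrate in more severe children.** This is plausible but undocumented.

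**Conclusion.** The concern holds in this limited form: treated and untreated children are pooled under common cut-offs, and ICS status plays no stated part in test timing, classification or analysis. On the protocol's own reasoning, treatment can move type 2 children below a cut-off, chiefly for FeNO.

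The size cannot be taken from the documents. Under the assumptions above, the observed risk ratio falls from about 1.56 to 1.32-1.50, or from about 1.72 to 1.48-1.67, provided that ICS does not itself change attack risk. These figures show scale and are not forecasts for this study.

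A reader might infer that children off ICS should supply the primary result. That does not follow. Off-ICS children are themselves selected by clinical judgement, and with 40% type 2 and 50-70% of those on ICS, only 12-20 type 2 children would remain (100 × 0.4 × 0.3 to 100 × 0.4 × 0.5).

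The change is worth making: it is cheap, and exact exposure on the day of testing is hard to rebuild later from a form that pools inhaled and oral steroid.

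**What to change.** Leave treatment with the child's clinician, and change only recording and reporting.

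1. **CRF, first test and retest.** Make sure that ICS and montelukast use are each recorded, separately from oral steroid: yes/no, start date, last dose.
2. **Section 11, main results.** Report biomarker positivity and each biomarker-attack association overall and by ICS status at the test, with ICS as a stratum or covariate. Do not make the off-ICS subgroup primary.
3. **Section 11, retest.** Report 3-month reproducibility separately for children whose ICS status did and did not change between the tests.
4. **Interpretation.** State whether each association describes prediction under usual care or the untreated phenotype.

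Cost: a few CRF fields at visits already planned, and the added stratified tables. Intervals within strata of 100 children will be wide, so the stratified results should be labelled descriptive.
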